1 CUHK Achilles Tendon Disorder Registry

2 **Research Project Statement**

3 The Achilles tendon is one of our body's most important structures, and the 'Achilles heel' is
4 a real clinical problem. The management of its pathologies—spanning acute ruptures to
5 chronic tendinopathies—remains heterogeneous, with a critical absence of high-quality
6 longitudinal data to compare treatments and guide personalized rehabilitation strategies. To
7 address this evidence gap, we will establish a comprehensive prospective Achilles Tendon
8 Disorder Registry.

9 The registry will integrate our team's expertise in Achilles tendon research, which
10 encompasses standardized assessment tools, biomechanical studies, and treatment evaluation.
11 By systematically collecting outcome data, it will enable us to: determine the effectiveness of
12 different treatment methods, advance evidence-based knowledge, improve the quality of care,
13 enhance patient safety, achieve better patient outcomes, and reduce healthcare costs. This
14 longitudinal registry will monitor long term outcome of Achilles tendon problem, and track
15 Achilles tendon treatment outcomes, thereby helping to inform precision rehabilitation
16 strategies and reduce long-term disability in the future.

17 **Research Questions**

- 19 1. Does the baseline status (e.g., vascularity and elastography metrics) influence the
20 prognosis?
- 21 2. Does pre-existing Achilles tendinopathy increase the risk of acute Achilles tendon rupture?
- 22 3. Which group of patients is more responsive to which treatment?

23 **Hypothesis**

- 25 1. Baseline status (e.g., vascularity and elastography metrics) significantly influences
26 prognosis.
- 27 2. Pre-existing Achilles tendinopathy significantly increases the risk of acute Achilles tendon
28 rupture.
- 29 3. Different patient groups respond differently to various treatment methods.

31 **Research Methodology**

32 **Study setting**

33 This prospective cohort study will be conducted at the Prince of Wales Hospital in Hong
34 Kong. All self-reported, functional, and ultrasonographic outcomes will be assessed at
35 baseline, 6 weeks, 3 months, 6 months, and 1 year. Following the initial 1-year follow-up, all
36 self-reported outcomes will be assessed annually through online questionnaires at 2, 3, 4, and
37 5 years. All participants must provide written informed consent prior to enrolment. The

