161 calcaneus. After the color signal stabilized for five seconds, the elastogram was recorded and
162 stored. Tendon stiffness was measured using a Q-box stiffness meter. Depending on the size
163 of the tendon, the diameter of the circular measuring area (Q-box) is set to 2 mm, which
164 covers the Achilles tendon and excludes other adjacent soft tissues. The Q-box is located in
165 the center of the maximum thickness point and 2, 4, 6 cm proximal to the calcaneal insertion
166 site. For each Q-box, the average tendon stiffness (in kPa) is measured.

167 **Tendon oxygenation and vascularity:** The pathological tendon's oxygenation and
168 vascularity were quantified using a multiwavelength photoacoustic ultrasound (PAUS)
169 system equipped with a 7Hz probe and dual-wavelength LED sources (850nm/750nm). The
170 participant assumes a prone position with heels extended beyond the examination table. The
171 probe is positioned on the target tendon, with mode-specific presets selected ("Deep PA" for
172 vascularity at 850nm; "Deep Oxy" for oxygenation at 750nm). Each 20-second acquisition
173 captures 200 frames, with two repeated scans per mode to ensure data reliability.

174 **Thermographic tendon temperature:** Participants will be advised to avoid physical
175 exercise and hot baths before the procedure to ensure data reliability. Each participant will
176 rest in a seated position for 10 minutes followed by 2 minutes without socks. The room will
177 be maintained at 20-24°C. The infrared camera will be positioned one meter from the
178 participant, using a ThermaCam FLIR-T8210. Images will be analyzed with ThermaCAM
179 Researcher Pro 2.8 SR-1 software, and a rectangular area covering the Achilles tendon will
180 be used for temperature assessment.

181

182 **Sample size**

183 As a prospective registry study, this study plans to consecutively enroll all eligible patients
184 presenting to the Prince of Wales Hospital between 2025 and 2028. Based on the annual
185 patient volume, a minimum of 500 participants is expected to be recruited, which is
186 anticipated to provide sufficient statistical power for the planned multivariable analyses.

187

188 **Recruitment**

189 Participants will be recruited through multiple concurrent strategies. Our primary recruitment
190 site is the Prince of Wales Hospital. We will also utilize our sports medicine network, which

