191 includes school sports teams, professional organizations (e.g., Kitchee Football Club), and an
192 extensive alumni network of doctors and sports medicine professionals from our MSc
193 program. Simultaneously, study advertisements will be distributed to all staff and students of
194 The Chinese University of Hong Kong through the CUHK Mass Mail System to ensure
195 comprehensive outreach.

196

197 **Data collection and management**198 **Plans to promote participant retention and complete follow-up:** The schedule for all the
199 outcome measure appointments will be provided from the beginning. For patients who have
200 missed their scheduled appointments for follow-up assessments, additional hours will be
201 extended to the evenings at the Sports Performance and Biomechanics laboratory at CUHK
202 so that participants may come for assessment (e.g., after work, rescheduled due to illness,
203 etc.).204 **Data management:** Data collected will be securely stored in password-protected computers
205 and archived for five years after publication. The Principal Investigator (PI) and research
206 assistants will oversee data collection, entry, and analysis. To ensure accuracy, a double data
207 entry method and range checks will be implemented. Data will be restored into an Excel files
208 and then transferred to SPSS software for analysis.209 **Confidentiality:** To ensure the highest level of privacy and security, the Sports Performance
210 and Biomechanics Laboratory stores all personal information and consent forms in securely
211 locked cabinets. Our online electronic database is protected by password-protected computers,
212 ensuring the utmost confidentiality. Access to the collected data is strictly limited to trusted
213 trial team members, with no access granted to participants. De-identified participant data may
214 be shared with other researchers upon reasonable request and after execution of appropriate
215 data sharing agreements, subject to approval by the ethics committee.

216 There is no plan for using biological specimens outside of this study plan.

217 **Statistical methods for primary and secondary outcomes:** Statistical analyses will be
218 performed using SPSS (version 28.0), with a two-sided significance level of $\alpha = 0.05$.
219 Continuous outcomes (e.g., VISA-A, NPRS, tendon thickness, dynamometry) will be
220 summarized as mean \pm standard deviation, assessed by Shapiro–Wilk test. Categorical

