221 variables will be presented as frequencies and percentages.222 To address Q1 (prognostic influence of baseline status), multivariable linear or logistic
223 regression models will be constructed to evaluate the association between baseline metrics
224 (e.g., vascularity, elastography) and functional outcomes (e.g., VISA-A, heel raise capacity),
225 adjusting for covariates such as age, sex, and symptom duration.226 For Q2 (risk assessment), a Cox proportional hazards model or logistic regression will be
227 used to examine whether pre-existing tendinopathy (dichotomized: yes/no) predicts
228 subsequent acute rupture, with results reported as hazard ratios or odds ratios and 95%
229 confidence intervals.230 For Q3 (treatment responsiveness), interaction terms between patient subgroups (e.g., defined
231 by baseline severity, structural metrics) and treatment types will be incorporated into
232 regression models to identify effect modifiers. Should significant interactions be detected,
233 stratified analyses will be performed.234 **Interim analyses:** An interim analysis will be performed on the primary endpoint when 20%
235 of participants completed the 1-year follow-up. The interim analysis ensures that no serious
236 adverse event happened during the study period.237 **Methods in analysis to handle protocol non-adherence and any statistical methods to
238 handle missing data:** Missing data will be handled using multiple imputation under the
239 missing-at-random assumption. Sensitivity analyses will include complete-case assessments.
240 Model assumptions (e.g., linearity, proportionality) will be verified graphically and
241 analytically.242 **Plans to give access to the full protocol, participant-level data, and statistical code:** The
243 protocol will be registered on clinicaltrials.gov. The participant-level data and statistical code
244 can be provided upon request.

245 **Oversight and monitoring:** The principal investigator will monitor the progress of the study.
246 The trial steering committee consists of research team members who will participate in
247 participant recruitment, data collection, and management. The trial steering committee
248 consists of orthopaedic surgeons and researchers (research assistants and biostatisticians).
249 The orthopaedic surgeons and research assistants will participate in data collection and
250 analysis. The biostatistician will monitor data collection and perform interim analysis. There

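### The Q1 prognosis model does not name baseline VISA-A, an outcome visit or a repeated-measures method, so a marker of current severity could be declared prognostic

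*Protocol*

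**What the plan says.** In the Protocol, under the statistical methods for primary and secondary outcomes, research question 1 is to be answered by "multivariable linear or logistic" regression. The baseline metrics (vascularity and elastography are the examples) are the predictors, functional outcomes (VISA-A and heel raise capacity are the examples) are the responses, and the model is fitted "adjusting for covariates such as age, sex, and symptom duration". Baseline VISA-A is not among the named covariates. Baseline severity does appear in the same section, but only as an example of a subgroup factor for research question 3.

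The Study setting section schedules all outcomes at "baseline, 6 weeks, 3 months, 6 months, and 1 year". After that, "self-reported outcomes will be assessed annually through online questionnaires at 2, 3, 4, and" 5 years. VISA-A is therefore measured at baseline and at eight follow-ups, and heel raise at baseline and at four. The Q1 text does not say which of these visits supplies the outcome and names no model for several scores from one person. VISA-A is classed as continuous, heel raise is recorded in seconds, and no rule says when logistic regression would be used.

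**The concern.** VISA-A at baseline measures how bad the tendon is on the day the imaging is done. By the Protocol's own descriptions, the vascularity grade is also an index of present disease: grade 0 is healthy and higher grades mean more vessels. If an imaging metric merely tracks present severity, and present severity predicts later VISA-A, the metric will be associated with later VISA-A without carrying any prognostic information of its own. Age, sex and symptom duration need not remove that association. The registry covers everything from acute rupture to chronic tendinopathy, so baseline severity is likely to vary widely.

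At stake is the meaning of a positive answer to research question 1. Without baseline VISA-A in the model, a significant coefficient cannot separate a marker that adds to what the questionnaire already shows from one that repeats it.

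The unfixed visit is a second weakness. With eight possible outcome scores, the analyst must either choose one later or use several. If several scores per person are put into ordinary regression as if independent, the standard error is too small.

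**Working it through.** **Figure in the plan.** The Sample size section says "patient volume, a minimum of 500 participants is expected to be recruited, which is" "anticipated to provide sufficient statistical power for the planned multivariable analyses". It gives no effect size, standard deviation or power, so there is no calculation to reproduce. I take n = 500 and the two-sided 5% level from the Protocol. All correlations below are assumptions, because the documents give none.

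**Visit count.** 6 weeks, 3 months, 6 months and 1 year make 4 follow-ups for all outcomes. Years 2, 3, 4 and 5 add 4 for self-reported outcomes. VISA-A: 4 + 4 = 8. Heel raise: 4.

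**Step 1: how often a marker with no added value is declared prognostic.** Let r be the correlation of marker with baseline VISA-A, and ρ that of baseline with follow-up VISA-A, both in absolute value. If the marker has no association with follow-up once baseline is held fixed, its unadjusted correlation with follow-up is r × ρ. With three covariates, the rejection probability by Fisher's z is Φ(d − 1.96) + Φ(−d − 1.96), where d = atanh(rρ) × √(500 − 3 − 3) = atanh(rρ) × 22.23.

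Example: r = 0.2 and ρ = 0.3 give rρ = 0.06, d = 0.0601 × 22.23 = 1.335, and Φ(−0.625) + Φ(−3.295) = 0.267.

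| r | ρ = 0.3 | ρ = 0.5 | ρ = 0.7 |
|---|---|---|---|
| 0 | 5% | 5% | 5% |
| 0.1 | 10% | 20% | 34% |
| 0.2 | 27% | 61% | 88% |
| 0.3 | 52% | 92% | 99.7% |

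With only 350 analysed, the row for r = 0.2 becomes 20%, 46% and 74%.

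**Step 2: check by simulation, with and without baseline VISA-A.** 2,000 runs of ordinary least squares at n = 500, ρ = 0.5, with three unrelated covariates:

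| r | without baseline VISA-A | with baseline VISA-A |
|---|---|---|
| 0.2 | 59% | 5.2% |
| 0.3 | 92% | 4.2% |

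The Monte Carlo standard error near 5% is √(0.05 × 0.95 / 2,000) = 0.5 percentage points, so both adjusted rates agree with the nominal 5%.

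**Step 3: eight scores in ordinary regression.** For a marker fixed within a person and equally correlated visits, the design effect is 1 + (m − 1) × ICC. With m = 8 it is 3.1 at ICC 0.3 and 5.9 at ICC 0.7. Stacking the visits as if independent gives a true type I error of 2 × [1 − Φ(1.96/√3.1)] = 27% and 2 × [1 − Φ(1.96/√5.9)] = 42%. For heel raise (m = 4) the figures are about 16% and 27%. Using one pre-set visit keeps type I error at 5% but discards the rest: the variance of the eight-visit mean is 3.1/8 = 0.39 to 5.9/8 = 0.74 of that of a single visit.

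**Step 4: does adjustment also sharpen the estimate?** Under the same null, the standard error of the marker coefficient with baseline VISA-A, relative to without, is √{(1 − ρ²) / [(1 − r²)(1 − r²ρ²)]}. At r = 0.2 this is 0.98, 0.89 and 0.74 for ρ = 0.3, 0.5 and 0.7. At r = 0.3 it is 1.00, 0.92 and 0.77. At r = 0.4 and ρ = 0.3 it is √[0.91 / (0.84 × 0.9856)] = 1.05, a small loss. Precision is therefore not the argument for the change.

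**The case against.** The strongest reply is that the covariates are given only as examples. Nothing excludes baseline VISA-A, and a statistical analysis plan that is not shown may add it. That stands: a reader might infer that the Protocol leaves the baseline score out by decision, and it does not say so. What can be said is that the Protocol's own Q1 specification names three covariates and not this one, although the score is already collected and baseline severity is thought of for research question 3.

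A second reply is that research question 1 asks only whether baseline status influences prognosis, not whether it does so beyond present symptoms. An association without baseline VISA-A answers that weaker question legitimately. If vascularity or stiffness drives symptoms, baseline VISA-A may lie on the pathway, and adjusting for it changes the question. This also stands, and it is why both models should be reported.

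Third, regression at one fixed visit is valid, so a mixed model is a better choice rather than a correction of an error. That is right for a fixed visit, but the Protocol fixes none.

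Three stronger readings are tempting but unsupported:

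- That VISA-A will be dichotomised. No cut-off or responder definition is stated, the outcomes are examples, and the Royal London Hospital test is a binary outcome for which logistic regression would be natural.
- That participants with a missed visit will be lost. The missing-data section plans multiple imputation, with complete-case analysis only as a sensitivity analysis.
- That adjustment brings a large gain in precision. The factor 1/(1 − ρ²) in effective sample size holds only if marker and baseline are uncorrelated, and in that case there is no false-positive problem to solve.

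**Conclusion.** The point holds as a weakness in a stated model that costs nothing to repair. As written, the Q1 analysis could declare a marker prognostic when it only reflects current severity. At n = 500 the chance is about 27% with correlations of 0.2 (marker with baseline) and 0.3 (baseline with follow-up), and 92% with 0.3 and 0.5. It is 5%, as it should be, if marker and baseline VISA-A are uncorrelated. With baseline VISA-A in the model it is about 5% throughout.

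A reader might infer that a false finding is bound to occur. The documents do not support that, because the size depends wholly on correlations they do not report. The unfixed visit adds a separate risk: inflated type I error if visits are stacked, or unused data and an open choice if one visit is picked.

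**What to change.** For VISA-A in research question 1, state a linear mixed model for repeated measures that uses all eight follow-up visits, with visit as a categorical factor, baseline VISA-A as a covariate alongside age, sex and symptom duration, and metric-by-visit terms. Name the 1-year contrast as the main estimate; the Protocol's interim analysis already ties the primary endpoint to the 1-year follow-up. Report the same model without baseline VISA-A beside it, and say what each answers: without it, whether the marker predicts outcome at all; with it, whether it predicts beyond current severity. State that logistic regression is used only for outcomes that are binary by nature.

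The cost is a few sentences of analysis text. No new data are needed, and SPSS 28, the planned software, has a mixed-model procedure. The change is best made before the interim analysis of the primary endpoint, planned when 20% of participants have completed 1 year.

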38 investigator will obtain and document consent before any study procedures are performed.
39 All eligible participants will be fully informed about the study and given ample time to
40 consider participation; the research team will answer all participant questions. The trial will
41 be conducted in accordance with the Declaration of Helsinki.

42 **Eligibility**

43 Inclusion:

- 45 • Adults (>18 years of age)

47

48 Exclusion:

49

50

51

52

53

54

- 55 Any physical or psychological comorbidity that would impair the ability to complete study assessments (e.g., significant neurological deficits) or preclude the provision of informed consent.
- Concomitant diseases that severely affect lower limb function or assessment (e.g., severe osteoarthritis of the knee or hip, prior lower limb amputation, peripheral vascular disease, active rheumatoid arthritis, lower limb paralysis, etc.)

56 **Outcome measures**

57 Baseline demographic data will be collected, including age (date of birth), gender (biological sex), occupation, recreational activity (Pre-injury and current activity levels -Tegner score), diagnosis (types of Achilles tendon problem) , treatment modalities already tried.

60 Time frames for collection include 0 weeks (baseline), 6 weeks, 3 months, 6 months, 1 year. Following the initial 1-year follow-up, all self-reported outcomes will be assessed annually through online questionnaires at 2, 3, 4, and 5 years.

64 **Primary Outcome: Victorian Institute of Sports Assessment (VISA-A) Questionnaire**

65 The primary outcome measure will be the Victorian Institute of Sport Assessment (VISA-A) questionnaire, available in either the original English or validated Chinese version, depending on the participant's native language. This specific scoring system developed for the Achilles tendon is the most widely used score for clinical Achilles research. The VISA-A is scored on a scale of 0 to 100; lower scores indicate more severity of symptoms, while a score of 100 indicates a healthy and pain-free Achilles tendon.

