72 **Secondary Outcomes: Numeric Pain Rating Scale (NPRS); Foot and Ankle Outcome Scores (FAOS); Achilles tendon resting angle (ATRA); Royal London hospital test; Calf Muscle Strength; Heel raise test; Jump test; Foot pressure distribution; Ultrasonographic tendon thickness; Ultrasonographic tendon cross-sectional area; Ultrasonographic neovascularity; Ultrasonographic tendon elasticity; Ultrasonographic calf muscle quality; Photoacoustic imaging-derived tendon oxygenation and vascularity; Thermographic tendon temperature.**

80 **Numeric Pain Rating Scale (NPRS):** The Numeric Pain Rating Scale (NPRS; 0–10, where 10 represents maximum pain) will be used to assess pain levels, as pain is the primary symptom of midportion Achilles tendinopathy. Participants will report their “Worst pain during sports in the past two weeks,” “Worst pain during daily activities in the past two weeks.”

86 **Foot and Ankle Outcome Scores (FAOS):** The FAOS is a validated patient-reported scoring system used for general foot and ankle problems. It is split into five categories: symptoms, pain, daily activities, sporting function, and quality of life. Scores range from 0 to 100, with 0 being the lowest and 100 being the highest.

90 **Achilles tendon resting angle (ATRA):** The ATRA will measure participants' tendon length/tension. Participants should be positioned in a prone position with the knee flexed to 90 degrees. The assessor will use a dynamic joint goniometer to measure the angle at which the foot passively falls.

94 **Royal London hospital test:** The Royal London Hospital Test is used to help diagnose mid-portion Achilles tendinopathy. The patient lies prone with the foot relaxed, and the examiner

96 palpates the most tender spot on the Achilles tendon. The patient then moves the ankle
97 through dorsiflexion and plantarflexion. A positive test occurs if tenderness decreases during
98 dorsiflexion.

99 **Calf Muscle Strength:** The hand-held dynamometer will be used to quantify isometric
100 muscle strength during ankle dorsiflexion and plantarflexion. Participants will maintain
101 maximal isometric contraction for 3 seconds. Three trials will be recorded for each movement,
102 with 30-second rest intervals between trials to prevent fatigue.

103 **Heel raise test:** Participants will be instructed to keep the knee straight and rise as high as
104 possible on the toes each time until fatigue. Participants can place two fingertips per hand on

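### Q2 models subsequent acute rupture, but the protocol specifies no collection of that event, and four of the five follow-up years have no stated route to detect or date it

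*Protocol*

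**What the plan says.** The Hypothesis section states as its second item: "Pre-existing Achilles tendinopathy significantly increases the risk of acute Achilles tendon" rupture. The Q2 paragraph under Statistical methods says that a Cox model or logistic regression will be "used to examine whether pre-existing tendinopathy (dichotomized: yes/no) predicts" the event, which it describes as "subsequent acute rupture, with results reported as hazard ratios or odds ratios and 95"% confidence intervals.

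What is collected, and when, is set out under Study setting and Outcome measures:

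- **Baseline.** "Baseline demographic data will be collected, including age (date of birth), gender (biological sex), occupation", activity level by Tegner score, "diagnosis (types of Achilles tendon problem") and treatments already tried.
- **Primary outcome.** VISA-A, a score from 0 to 100.
- **Secondary outcomes.** A list of 15 items, beginning "Secondary Outcomes: Numeric Pain Rating Scale (NPRS); Foot and Ankle Outcome Scores (FAOS); Achilles tendon resting angle (ATRA"), and continuing with clinical and performance tests, foot pressure, ultrasound, photoacoustic and thermographic measures.
- **Schedule.** Self-reported, functional and ultrasound assessment at baseline, 6 weeks, 3 months, 6 months and 1 year. Then: "Following the initial 1-year follow-up, all self-reported outcomes will be assessed annually through online questionnaires at 2, 3, 4, and 5 years".

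The section on adverse events provides for reporting severe reactions to the intervention to the steering committee.

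**The concern.** Q2 is one of three stated research questions and has its own hypothesis and model. Both candidate models need a recorded rupture for each participant or tendon. The Cox option also needs a date. If the exposure and the event are to be tied to the same tendon, the side is needed as well. The protocol specifies none of these three fields.

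This differs from detail that a protocol may leave to an analysis plan. A plan written later can choose between Cox and logistic regression, define who is at risk and say how re-rupture is handled. It cannot supply an event that no visit or questionnaire recorded. Enrolment is planned for 2025 to 2028, so the gap grows with each contact that passes without the question. If the schedule is followed as written, Hypothesis 2 would rest mainly on ruptures that come to light at in-person visits in the first year.

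**Working it through.** The protocol gives no figure to reproduce on this point: no rupture rate, expected number of ruptures or hazard ratio. The check is therefore a comparison of what Q2 needs with each place where the protocol says what is collected.

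| Place in the protocol | What it records | Does it specify a subsequent rupture, its side or its date? |
|---|---|---|
| Baseline data | Type of Achilles problem at entry | No. It can show a rupture present at entry, which is not a subsequent event. Previous rupture and side are not named. |
| Primary outcome | VISA-A, 0 to 100 | No |
| Secondary outcomes, 15 items | Pain, function, clinical tests, imaging, temperature | No item is rupture |
| Visits at 6 weeks, 3, 6 and 12 months | The outcomes above, with both Achilles tendons imaged | Not specified, though the examination may reveal a rupture |
| Questionnaires at 2, 3, 4 and 5 years | Self-reported outcomes; those described are VISA-A, NPRS (0 to 10) and FAOS (five categories) | No |
| Adverse events | Severe reactions to the intervention | No. A rupture during ordinary follow-up need not be one. |

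**Share of follow-up affected.** Scheduled follow-up is 5 years and the last in-person assessment is at 1 year. Questionnaire-only share = (5 − 1)/5 = 0.80, or 4 of 5 years.

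**Illustration in events, with assumed rates.** The protocol gives only the minimum of 500 participants. Assume that all 500 are at risk, with no dropout and a constant rupture rate. Events = 500 × rate × years.

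| Assumed rate per year | Year 1 | Years 2 to 5 | Five years |
|---|---|---|---|
| 0.5% | 500 × 0.005 × 1 = 2.5 | 500 × 0.005 × 4 = 10 | 12.5 |
| 1% | 500 × 0.01 × 1 = 5 | 500 × 0.01 × 4 = 20 | 25 |
| 2% | 500 × 0.02 × 1 = 10 | 500 × 0.02 × 4 = 40 | 50 |

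The 80% split follows from the constant-rate assumption and is not evidence about actual rupture rates. If risk is concentrated in the first year, the share falling later is smaller. No power figure is derived: every input would be assumed, and the usual normal approximation cannot be trusted at counts as low as 2.5.

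**The case against.** The strongest reply is that the protocol's lists are not the whole data set. The baseline list is introduced as a set of inclusions and need not be exhaustive. Q1 adjusts for symptom duration, which that list does not name either. The case report forms are not shown and may already ask about rupture. Participants are seen four times after baseline in the first year, with both tendons scanned, so year-1 ruptures would not go unseen merely for lack of a named field. Logistic regression needs no date.

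Much of this stands for year 1 and is why the point is not put as a complete absence of data. It does not reach years 2 to 5. There the protocol says that the self-reported outcomes are what is collected, and none of those described is a rupture item. Logistic regression still needs the event itself.

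Three stronger readings might be inferred, and the documents do not support them.

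- *That Q2 will mix first ruptures with re-ruptures.* The Research Project Statement does say "The management of its pathologies—spanning acute ruptures to" chronic tendinopathies, but that sentence describes the field. The visible inclusion list is incomplete in the available text. Enrolment of ruptured tendons is likely, but it is inferred from that statement and the baseline diagnosis field. The risk set, the unit of analysis and clustering may properly be set in the analysis plan. Any figure for distortion would rest wholly on invented inputs and could go in either direction.
- *That 500 participants are too few for Q2.* The Sample size section speaks of the planned multivariable analyses, and the statistical section uses that word only for Q1. For Q2 the statement is at most unsupported; it is not disproved.
- *That Q2 cannot be answered at all.* Year-1 visits may yield some events, and unseen forms may yield more.

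**Conclusion.** The point holds for event collection. Q2 names an event that no listed outcome, follow-up visit, later questionnaire or safety route is specified to record. The gap is firmest in years 2 to 5, which make up 80% of scheduled follow-up time per participant. In year 1 it is a matter of unspecified rather than impossible capture.

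The conclusion rests on reading the outcome lists and schedule as the stated collection plan, and on the case report forms being unseen. If those forms already record rupture, side and date at every contact, the remaining defect is only that the protocol does not say so. The event counts shown are illustrations under assumed rates and carry no weight in the conclusion. The protocol should be changed, because the loss cannot be repaired at analysis, but the harm is limited to Q2 and Hypothesis 2. VISA-A as primary outcome is not affected.

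**What to change.** 1. Add incident Achilles tendon rupture (yes/no, side, date) to the listed outcomes, to be asked at the 6-week, 3-month, 6-month and 1-year visits and in the 2-, 3-, 4- and 5-year questionnaires.
2. State that self-reported ruptures will be checked against existing hospital records where these are available.
3. Add previous or current rupture, with side, to the baseline data, so that first rupture and re-rupture can be told apart at analysis.

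Who is at risk, whether the unit is the person or the tendon, and how two tendons from one person are handled may be left to the analysis plan. These items give it the data to work with. No change to the sample size statement is asked for on this ground.

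The cost is a few extra items on existing forms and questionnaires, some record checking and a protocol amendment, with no extra visits or participants. Some later events will still rest on self-report alone. This is likelier for people recruited through the sports and university networks, whose care may be elsewhere. Dates recalled at an annual questionnaire will also be less exact than those taken at a visit.
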